3.4.3 Off Protocol Therapy and Off-Study Procedure

Authorized staff must notify Central Registration Office (CRO) when a subject is taken off protocol therapy and when a subject is taken off-study. A Participant Status Updates Form from the web site (<http://home.ccr.cancer.gov/intra/eligibility/welcome.htm>) main page must be completed and sent via encrypted email to: NCI Central Registration Office [contact].

4 DATA COLLECTION AND EVALUATION

4.1 DATA COLLECTION

All data will be kept secure. The PI will be responsible for overseeing entry of data into an in-house password protected electronic system and ensuring data accuracy, consistency and timeliness. The principal investigator, associate investigators/research nurses and/or a contracted data manager will assist with the data management efforts. All human subjects personally identifiable information (PII) as defined in accordance to the Health Insurance Portability and Accountability Act, eligibility and consent verification will be recorded. Primary data obtained during the conduct of the protocol will be kept in secure network drives or in approved alternative sites that comply with NIH security standards. Primary and final analyzed data will have identifiers so that research data can be attributed to an individual human subject participant.

All AEs, including clinically significant abnormal findings on laboratory evaluations, regardless of severity, will be followed for 30 days or until return to baseline or stabilization of event.

Abbreviated Title: RFA + TACE with RO Beads

Version Date: 04/13/2018

Serious adverse events that occur more than 30 days after the last administration of investigational agent/intervention and have an attribution of at least possibly related to the agent/intervention should be recorded and reported.

An abnormal laboratory value will be considered an AE if the laboratory abnormality is characterized by any of the following:

- Results in discontinuation from the study
- Is associated with clinical signs or symptoms
- Requires treatment or any other therapeutic intervention
- Is associated with death or another serious adverse event, including hospitalization.
- Is judged by the Investigator to be of significant clinical impact
- If any abnormal laboratory result is considered clinically significant, the investigator will provide details about the action taken with respect to the test drug and about the patient's outcome.

End of study procedures: Data will be stored according to HHS and FDA regulations, and NIH Intramural Records Retention Schedule as applicable.

Loss or destruction of data: Should we become aware that a major breach in our plan to protect subject confidentiality and trial data has occurred, the IRB will be notified.

4.1.1 Baseline Data Collection

Following consent, participating patients will typically undergo a CT of the chest abdomen, and pelvis, as clinically warranted. Additional imaging may be obtained if clinically indicated by the treating interventional radiologist, to identify the target area. Previous imaging may also be used as baseline scans if they fall within the allowed protocol timeframe. Standard baseline information which typically includes demographics, disease history, and previous therapy for liver malignancies will be collected.

4.1.2 On Study Data Collection

We will also document bead visibility data during embolization. This information will be collected using a qualitative particle visibility scale by applying a 3-point scale: 0, definitely not visible; 1, probably visible; and 2, definitely visible [21].

Intra-procedural, post treatment, and follow up images will all be saved and stored in PACS. Patient images will be anonymized prior to transfer to a secure work station for analysis. CRF's and non-image data will be stored in the DRD shared drive which has limited access. The DRD shared drive is backed up and managed by the NIH DCRI in keeping with the protection and confidentiality guideline of the Privacy Act of 1974.

Any grade 3 events and higher occurring up to 72 hours post treatment (either with combined RFA and TAE or with TAE alone) will be collected and recorded in the study database as adverse events, except those listed in the Exclusions to Adverse Event Data Collection section (see Section 4.1.3). Grade 2 events will be collected and recorded if not resolved before the patient is considered off treatment (72 hours post treatment). Grade 1 events will not be collected or reported.

Abbreviated Title: RFA + TACE with RO Beads

Version Date: 04/13/2018

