5.1.2 Adverse Device Effect

An adverse device effect (ADE) is an AE related to the use of the LC Lumi Radiopaque embolic beads.

Serious Adverse Event (SAE) is an AE that results in the following:

- death
- serious deterioration of the subject's health, leading to
 - life-threatening illness or injury, or
 - permanent impairment of a body structure or function, or
 - in-patient or prolonged hospitalization, or
 - medical or surgical intervention to prevent life-threatening illness or injury or permanent impairment of a body structure or function
- fetal distress, fetal death or a congenital abnormality or birth defect

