5.2.2 NCI-IRB Requirements for PI Reporting at Continuing Review

The protocol PI will report to the NCI-IRB:

1. A summary of all protocol deviations in a tabular format to include the date the deviation occurred, a brief description of the deviation and any corrective action.
2. A summary of any instances of non-compliance
3. A tabular summary of the following adverse events:
 - All Grade 2 **unexpected** events that are possibly, probably or definitely related to the research;
 - All Grade 3 and 4 events that are possibly, probably or definitely related to the research;
 - All Grade 5 events regardless of attribution;
 - All Serious Events regardless of attribution.

NOTE: Grade 1 events are not required to be reported.

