- Presence of high-flow arteriovenous shunt with a diameter greater than the selected bead size that cannot be coiled or blocked.
- Do not use LC Bead LUMI™ in the following applications:
 - Embolization of arteriovenous (AV) shunts (i.e. where the blood does not pass through the arterial/capillary/venous transition but directly from artery to vein).
 - Any vasculature where LC Bead LUMI™ could pass directly into the internal carotid artery or other non-target territories.
 - Any neurovascular indication.
- Do not use in the pulmonary arterial vasculature.

CAUTIONS:

- Embolization with LC Bead LUMI™ should only be performed by physicians who have received appropriate interventional occlusion training in the anatomical region intended to be embolized.
- Do not use if the vial or packaging appears damaged.
- Sterile and single-use product. Do not reuse due to risk of infection.
- If there are any symptoms of unwanted embolization during injection, consider stopping the procedure to evaluate the possibility of shunting. Such symptoms may include changes in patient's vital signs, such as hypoxia or central nervous system changes.
- In case of hypersensitivity to contrast agents it is recommended not to use LC Bead LUMI™.
- Consider upsizing LC Bead LUMI™ in the presence of AV shunts if angiographic evidence of embolization does not appear quickly during delivery.
- Use only the recommended non-ionic contrast agents (see Table 2).
- Non-target embolization may occur in the presence of arteriovenous anastomosis, branch vessels which lead away from the targeted embolization area, or emergent vessels not evident prior to embolization. The patient may experience severe complications as a result of non-target embolization. Special care should be taken to avoid ischemia of non-tolerant, non-targeted tissue.
- Patients with prior biliary surgery, bile duct dilation or vessels close to bile ducts may be at increased risk from infection (e.g. biloma/ liver abscess).
- Consideration should be given to Tc99m-MAA scanning if there is suspicion of AV shunting, especially when using the smaller bead sizes.
- Risks of radiation from angiography and fluoroscopy used to visualise the blood vessels during embolization which may include a radiation burn and risks to future fertility.
- A maximum of 4 vials of LC Bead LUMI™ can be used in a single treatment session.

CAUTION:

Federal (USA) law restricts this device to sale by or on order of a physician.

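### Section 4.1.2 leaves out grade 2 events that resolve within 72 hours, yet section 5.2.2 requires all unexpected, related grade 2 events, so the study database cannot assure a complete continuing-review table

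*Combined protocol and SAP*

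**What the plan says.** Section 4.1.2 sets out what enters the study database, by grade.

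- Grade 3 and above: "Any grade 3 events and higher occurring up to 72 hours post treatment", less the expected events exempted in section 4.1.3.
- Grade 2: "Grade 2 events will be collected and recorded if not resolved before the patient is considered off treatment (72 hours post treatment").
- Grade 1: neither collected nor reported.

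Section 5.2.2 sets out what the principal investigator must tabulate for the IRB at continuing review. For grade 2 it asks for "All Grade 2 unexpected events that are possibly, probably or definitely related to the research". It also asks for related grade 3 and 4 events, grade 5 events whatever the attribution, and "All Serious Events regardless of attribution". Grade 1 events need not be reported. None of these lines depends on how long an event lasted.

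Section 4.1 adds that all adverse events, "regardless of severity, will be followed for 30 days or until return to baseline or stabilization of event". Section 4.1.4 likewise speaks of following events, and has the investigator judge seriousness and causality for those that are reported.

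**The concern.** For grade 1 the recording and reporting rules agree: nothing is collected and nothing is due. For grade 2 they do not. Recording turns on persistence to 72 hours. Reporting turns on unexpectedness and attribution. An event can meet the reporting test and fail the recording test.

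What is at stake is capture of short-lived, possibly device-related events around the procedure. Section 5.4.1 says that decisions about ongoing enrollment and intervention rest on toxicity data from earlier patients, and the IRB relies on the continuing-review table. A rule that keeps only persistent grade 2 events can lower the count but never raise it.

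**Working it through.** The plan states no figure on this point, so the check is a comparison of texts.

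**Step 1: cross the two rules for grade 2 events not listed in section 4.1.3.**

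| Unlisted grade 2 event | Recorded under 4.1.2? | Due as a grade 2 event under 5.2.2? |
|---|---|---|
| Unexpected, related, unresolved at 72 h | Yes | Yes |
| Unexpected, related, resolved by 72 h | No | Yes |
| Expected or unrelated, unresolved at 72 h | Yes | No |
| Expected or unrelated, resolved by 72 h | No | No |

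The second row is the gap. The grade 2 sentence does not contain the word *only*, but its condition would have no purpose if resolved events were also to be recorded.

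**Step 2: look for text that closes the gap.**

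- Sections 4.1 and 4.1.4 promise follow-up. Neither says that the event is entered in the database.
- The section 4.1.3 exception, for events that the principal investigator judges unexpected, applies only to the events listed there.
- Section 4.3.1, on evaluability for toxicity, mentions only grade 3 or greater.
- Sections 5.1.9 and 5.2.1 send unanticipated problems to the IRB within 7 days. An event must be unexpected, at least possibly related, and also suggest greater risk than was previously known. That third condition makes the class narrower than the grade 2 line in section 5.2.2.
- Section 5.3 covers reports to the manufacturer of device malfunctions and of unanticipated serious events that are at least possibly related.

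None of these covers the second row as a whole.

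**Step 3: serious events, a secondary point.** The definition of a serious event, placed in section 5.1.2, does not depend on grade; one criterion is "in-patient or prolonged hospitalization, or". A grade 2 event could therefore be serious. To be lost through the grade 2 rule it would have to be serious and also resolve by 72 hours. Larger losses come from elsewhere: the section 4.1.3 exclusions, which apply at grade 3 and above as well; the 72-hour limit on collection; and the section 4.1 rule that, after day 30, only serious events at least possibly related are recorded.

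**Step 4: size.** No rate of unexpected, related, transient grade 2 events is given. As an assumption only, let p be the chance per treated patient of at least one such event. The chance that at least one of n patients has one is 1 − (1 − p)^n, shown for the 20 evaluable and 30 enrolled patients planned:

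| Assumed p | n = 20 | n = 30 |
|---|---|---|
| 1% | 18% | 26% |
| 2% | 33% | 45% |
| 5% | 64% | 79% |
| 10% | 88% | 96% |

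For example, 1 − 0.98^30 = 0.455. These are chances that an event falls outside the recording rule, not that it is missing from the IRB table, because the chart may supply it.

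**The case against.** The best defence is that section 4.1.2 limits study data collection and does not cancel the reporting duty in section 5.2.2. Patients are inpatients after the procedure, typically with daily laboratory tests (section 3.2.2). The team discusses each patient, and the principal investigator reviews each patient's adverse event data (section 5.4.1) and watches continuously for unusual complications (section 5.4.2). This stands as far as it goes. A reader might infer that the table cannot be complete, and the documents do not support that: it is incomplete only if such an event occurs and is overlooked. But nothing requires the chart to carry the judgments of attribution and expectedness that section 5.2.2 needs, and section 4.1.4 calls for the causality judgment on reported events. The mismatch remains.

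Three other stronger readings are tempting.

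- *The grade 2 rule is why serious events would be missing.* It is at most a minor cause, as step 3 shows.
- *Early signs of bead passage are what would be lost.* The device instructions in Appendix C say of unwanted embolization: "Such symptoms may include changes in patient's vital signs, such as hypoxia or central nervous system changes". That caution concerns signs during injection and is not a data-capture rule. The same instructions list pulmonary embolization, stroke and neurological deficits as potential complications, so these signs are arguably described risks rather than unexpected events.
- *A count of missing events can be given.* It cannot. Many common procedural events are listed as expected in section 4.1.3, and nothing in the documents indicates how often unexpected ones occur.

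The consequences are also limited. The sole stated objective is imaging, and the analysis is descriptive. Section 9.1 does call this a safety and feasibility study, but in a subject-selection rationale; no safety objective is stated. The stopping rules in section 3.2.4 use non-laboratory grade 4 toxicity and death, which the grade 2 rule does not touch.

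**Conclusion.** The point holds in a narrow form. Sections 4.1.2 and 5.2.2 disagree for one class: unlisted, unexpected, at least possibly related grade 2 events that resolve within 72 hours. This is a conflict between two stated rules, not missing detail. Completeness of the grade 2 part of the continuing-review table is not assured from the study database, and any error is toward under-counting. Its size cannot be derived from the documents; the probabilities above rest wholly on assumed rates. The conclusion assumes that staff apply the section 4.1.2 condition as written and that no other study record is required to capture these events; the protocol names none.

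**What to change.** In section 4.1.2, state that a grade 2 event judged unexpected and at least possibly related to the research or the device is recorded whether or not it has resolved by 72 hours, and that other grade 2 events are recorded only if unresolved at that time. This alone closes the grade 2 gap.

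If the same amendment is to cover serious events of any grade, so as to serve the serious-event line of section 5.2.2, then sections 4.1, 4.1.3 and 4.3.1 must be reconciled with it. Otherwise section 4.1.3 would still exempt listed events that section 4.1.2 newly required, and one contradiction would replace another.

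The cost is one sentence, a few more CRF lines, and a slightly higher reported count of grade 2 events. The change concerns recording only. It leaves clinical management, the stopping rules and the imaging objective as they are.

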4.1.3 Exclusions to Adverse Event Data Collection

The following adverse events are expected events from the procedure and study device and will not be collected unless the nature, severity, and frequency are deemed by the PI as unexpected for this patient population.

Anticipated adverse events related to TAE:

- Fever
- Right upper quadrant pain
- Acute cholecystitis
- Acute pancreatitis or elevation of amylase and lipase
- Nausea
- Vomiting
- Fatigue
- Elevated white blood cell count
- Elevated liver enzymes
- Bleeding
- Groin hematoma
- Arterial dissection
- Portal vein thrombosis
- Pleural effusions
- Aspiration pneumonia from intubation
-

Anticipated adverse events related to ablation procedure:*

- Pain at the site of ablation needle insertion
- Muscle ache
- Fever
- Fatigue
- Nausea
- Vomiting
- Elevated liver function tests
- Hyponatremia following hydro-dissection
- Thrombocytopenia and anemia post-RFA
- Pleural effusions
- Aspiration pneumonia from intubation
- Bleeding

*If ablation is given

Anticipated adverse events related to LC LUMI beads (will collect if grade 3 or above):

- Allergic reaction to LC LUMI beads

Abbreviated Title: RFA + TACE with RO Beads

Version Date: 04/13/2018

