3.2.4 Study Stopping Rules

Enrollment will be halted and the IRB notified if:

- Three or more patients with a non-laboratory grade 4 toxicity within the first 72 hours post TAE whether or not considered TAE or research-related.
- Death due to any cause within the first 72 hours post TAE.

All patients will be monitored until there is improvement or resolution of toxicity. Once the IRB, has completed their review; they must give their permission for the study to resume.

Abbreviated Title: RFA + TACE with RO Beads

Version Date: 04/13/2018

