4.3 RESPONSE CRITERIA

4.3.1 Definitions

- Evaluable for bead visibility: All patient imaging will be evaluated for the visibility of the LC LUMI beads using a 3 point scale: 0, definitely not visible; 1, probably visible; and 2, definitely visible as defined the treating interventional radiologists. Other characteristics may be noted such as the radiopacity of the beads, visibility of the beads in the tumor, overall location of beads in relation to the tumor or targeted site.
- Evaluable for toxicity: All patients will be evaluable for toxicity from the time of their treatment with LC LUMI radiopaque beads up to 72 hours post completion of treatment. Grade 3 or greater adverse events, including allergic reactions, collected during this time period, will be followed until resolution. Expected or anticipated adverse events from the research or the study device will not be collected. See Section **4.1.3** for details.
- Evaluable for imaging characteristics: Only those patients who are eligible for the study, have received at least one treatment of TAE, and have had their disease re-evaluated per standard of care imaging will be considered evaluable.

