5.4 DATA AND SAFETY MONITORING PLAN

5.4.1 Principal Investigator/Research Team

The clinical research team will meet on a routine basis when patients are being actively treated on the trial to discuss each patient. Decisions about ongoing enrollment and intervention will be made based on the toxicity data from prior patients.

All data will be collected in a timely manner and reviewed by the principal investigator or a lead associate investigator. Adverse events will be reported as required above. Any safety concerns, new information that might affect either the ethical and or scientific conduct of the trial, or protocol deviations/reportable events will be immediately reported to the IRB using iRIS.

The principal investigator will review adverse event and response data on each patient to ensure safety and data accuracy. The principal investigator will personally conduct or supervise the investigation and provide appropriate delegation of responsibilities to other members of the research staff.

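### The enrollment halt counts every non-laboratory grade 4 toxicity within 72 hours, but listed procedural events go uncollected at any grade unless the PI finds them unexpected, so the count can fall short.

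*Combined protocol and SAP*

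**What the plan says.** Section 3.2.4 stops enrollment and notifies the IRB under two limbs. The first is "Three or more patients with a non-laboratory grade 4 toxicity within the first 72 hours post TAE whether or not considered TAE" or research-related. The second is any death in the same 72 hours. Neither limb exempts anticipated events.

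Section 4.1.2 governs data capture over those 72 hours. Events of grade 3 and higher "will be collected and recorded in the study database as adverse events, except those listed in the Exclusions to Adverse Event Data Collection section". Section 4.1.3 says the listed events "will not be collected unless the nature, severity, and frequency are deemed by the PI as unexpected for this patient population". Its TAE and ablation lists state no grade limit. The bead list, which holds only allergic reaction, does: "Anticipated adverse events related to LC LUMI beads (will collect if grade 3 or above". Section 4.3.1, in defining who is evaluable for toxicity, repeats the exclusion: "Expected or anticipated adverse events from the research or the study device will not be collected".

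Two further sections depend on these data. Section 5.4.1 says: "Decisions about ongoing enrollment and intervention will be made based on the toxicity data from prior patients". Section 5.2.2 requires a table for the IRB at continuing review that includes "All Grade 3 and 4 events that are possibly, probably or definitely related to the research" and "All Serious Events regardless of attribution".

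**The concern.** The halt rule and the data meant to feed it do not cover the same events. The rule counts all non-laboratory grade 4 toxicity; the collection rules leave out a set of procedural complications, several of which can be severe. Two people applying the protocol to the same patients could reach different counts, depending on whether they count listed events. Enrollment could then continue after three patients had met the stated criterion.

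The table required by Section 5.2.2, and any adverse event summary at the end of the study, could also omit grade 3-4 events of the listed types. Section 9.1 describes the trial as a safety as well as a feasibility study, and Section 3.4.1 refers to Section 3.2.4 for its definition of unacceptable toxicity, so the ambiguity extends beyond the halt itself.

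**Working it through.** **1. Coverage over the first 72 hours**

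| Section | Event scope | Grade | Exemption for expected events |
|---|---|---|---|
| 3.2.4, first limb | Non-laboratory toxicity, any attribution | 4 | None |
| 4.1.2 | Adverse events recorded in the database | 3 and higher (grade 2 only if unresolved at 72 hours) | Events listed in 4.1.3 |
| 4.1.3, TAE and ablation lists | Not collected, subject to the PI exception | No limit stated | The lists themselves |
| 4.1.3, bead list | Allergic reaction | Collected at 3 and higher | None at those grades |
| 4.3.1 | Toxicity evaluation | 3 and higher | Expected or anticipated events |
| 5.2.2 | IRB table | Related 3-4; all serious events | None |

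The laboratory items on the lists do not matter here, because the first limb ignores laboratory toxicity. The non-laboratory items include bleeding, acute cholecystitis, acute pancreatitis, arterial dissection, portal vein thrombosis, pleural effusions and aspiration pneumonia.

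**2. Is a grade limit implied?** No. Section 4.1.2 applies the exclusion directly to grade 3 and higher events, and Section 4.1.3 writes a grade limit for beads but none for TAE or ablation.

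**3. The plan's own figure.** The plan derives no figure for the halt rule. Its only derived number is the recruitment total in Section 7.0: 20/(1 - 0.33) = 29.85, rounded up to 30. This reproduces. I use 20 and 30 as the range for the number treated.

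**4. Illustration of size.** Let p be the true per-patient rate of non-laboratory grade 4 toxicity within 72 hours, and s the share of affected patients whose only such events are on the lists. The documents give neither, so both are assumed. The rate counted is q = p(1 - s), and

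P(at least 3 counted) = 1 - Σ(k = 0 to 2) C(n,k) q^k (1 - q)^(n - k).

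For n = 30 and q = 0.10: 1 - (0.0424 + 0.1413 + 0.2277) = 0.589.

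| n treated | p | s = 0 | s = 25% | s = 50% |
|---|---|---|---|---|
| 30 | 20% | 0.956 | 0.849 | 0.589 |
| 30 | 10% | 0.589 | 0.393 | 0.188 |
| 20 | 20% | 0.794 | 0.595 | 0.323 |
| 20 | 10% | 0.323 | 0.186 | 0.075 |

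Because the count only accumulates, this is also the chance of reaching three at any point up to n.

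A version that needs no assumed rate: if exactly three patients have a grade 4 event and each is captured independently with probability 0.75 or 0.50, all three are counted with probability 0.75³ = 0.422 or 0.50³ = 0.125.

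**The case against.** The best defence is that Section 3.2.4 does not say its count comes from the study database. It counts patients with a toxicity, and Section 4.1.3 limits only what is collected. Patients are inpatients after the procedure (Section 3.2.2), the team discusses each one (Section 5.4.1), and the PI monitors safety continuously at a single center (Section 5.4.2). On that reading every grade 4 event is already known and counted, and only a cross-reference is missing. That reading is possible, but no section says that a listed event, once known, is recorded or counted. Section 5.4.2 directs the PI to unusual or unpredicted complications, which listed events are not.

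Second, the PI exception could bring in a severe listed event. It could, so under-counting is possible rather than certain. But the exception is discretionary, joins nature, severity and frequency with *and*, and asks for a view on the frequency of events that are not being collected.

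Third, other text points toward capture. Section 4.1 says all adverse events are followed for 30 days or until they return to baseline or stabilize. Section 5.1.2 makes life-threatening illness or injury serious, so many grade 4 events would fall under the Section 5.2.2 duty to tabulate. But following an event is not counting it toward the halt, and the Section 5.2.2 table is periodic. It also asks for events that Section 4.1.3 says not to collect, so it adds a conflict instead of curing the first.

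Two criticisms stand. The probabilities rest on assumed rates and shares, and assume that neither the PI exception nor any other route adds the event; the case must rest on the text. And confining the exclusions to grades 1-2 would leave Section 4.1.3 little to do, since grade 1 is never collected and grade 2 only if unresolved at 72 hours.

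**Conclusion.** The concern holds. The first limb of Section 3.2.4 covers events that Sections 4.1.2, 4.1.3 and 4.3.1 leave out of collection in the same window, and nothing routes them back into the count. The conclusion rests on the wording alone. If a quarter to a half of affected patients had only listed events and these went uncounted, the chance of reaching three with 30 treated would drop by about 0.11 to 0.37 at a true rate of 20% (0.956 - 0.849; 0.956 - 0.589) and by about 0.20 to 0.40 at 10% (0.589 - 0.393; 0.589 - 0.188).

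The limits are clear. The any-cause death limb is not affected. Bead allergy at grade 3 or above is collected, and harms in the Section 9.5 risk table that are not on the lists, such as liver failure and liver abscess, remain collectable. The descriptive imaging objective is untouched. This should be fixed, because it concerns the trial's only explicit enrollment halt.

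**What to change.** Reconcile Sections 3.2.4, 4.1.2, 4.1.3, 4.3.1 and 5.2.2.

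- **Preferred:** confine the Section 4.1.3 exclusions to non-serious events of grade 1-2, and bring Sections 4.1.2 and 4.3.1 into line. This repairs the halt count and removes the conflict with Section 5.2.2.
- **Minimum:** add one sentence saying that every non-laboratory event of grade 4 or higher within 72 hours of TAE is recorded, and counted toward whichever limb of Section 3.2.4 it meets, whether or not Section 4.1.3 lists it. This repairs the halt count but leaves the grade 3 gap against Section 5.2.2.

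Neither option changes the halt thresholds; a death within 72 hours already triggers the second limb. Since Section 3.4.1 relies on Section 3.2.4, the sponsor should check that the two still read consistently.

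The cost is wording in three sections, or one sentence, plus added case report form entries for at most 30 patients who are already monitored in hospital. The number of entries cannot be estimated without event rates. The preferred option largely reverses the choice not to collect expected procedural events, and the reported adverse event profile may look less favorable.

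### Sections 4.1.2, 4.1.3 and 4.3.1 by default keep listed TAE and ablation events out of the adverse-event database at any grade, while section 5.2.2 requires a table of all related grade 3 and 4 events

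*Combined protocol and SAP*

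**What the plan says.** Three sections restrict what enters the adverse-event database.

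- Section 4.1.2 collects grade 3 and higher events up to 72 hours after treatment, "except those listed in the Exclusions to Adverse Event Data Collection section".
- Section 4.1.3 gives separate lists for TAE, for ablation (if given) and for the beads. Listed events "will not be collected unless the nature, severity, and frequency are deemed by the PI as unexpected for this patient population". The TAE list includes "Elevated liver enzymes" and the ablation list includes "Elevated liver function tests". Neither list states a grade. The bead list, whose one entry is allergic reaction, does: "Anticipated adverse events related to LC LUMI beads (will collect if grade 3 or above").
- Section 4.3.1, in the definition of evaluable for toxicity, repeats the exclusion: "Expected or anticipated adverse events from the research or the study device will not be collected".

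Section 5.2.2 sets what the investigator must tabulate for the IRB at continuing review. For grade 2 the line is "All Grade 2 unexpected events that are possibly, probably or definitely related to the research". For the higher grades it is "All Grade 3 and 4 events that are possibly, probably or definitely related to the research". The limit to unexpected events appears only in the grade 2 line. Section 5.2.2 does not refer to 4.1.3.

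**The concern.** The two sets of instructions give different answers for the same event. A related grade 3 or 4 event that is on a 4.1.3 list and judged expected is not collected, yet it belongs in the 5.2.2 table. No section says how an event left out of the database would reach that table. Section 4.1.4 describes the assessment of causality for reported events, and 5.2.2 depends on that assessment.

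At stake is the completeness of the adverse-event table. Its reader could not tell whether a listed grade 3 or 4 event did not occur or was not collected. Two members of staff, one working from 4.1.3 and one from 5.2.2, would produce different tables from the same patients.

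**Working it through.** The plan states no figure on this point. Its recruitment total reproduces, 20 / (1 − 0.33) = 29.85, rounded up to 30, but the argument does not use it. The check is a count and a comparison of sections.

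**1. Entries without a grade limit (section 4.1.3).** TAE 15 + ablation 12 + beads 1 = 28. With a grade limit: 1 (bead allergy). Without: 28 − 1 = 27. Seven events stand on both the TAE and ablation lists (fever, fatigue, nausea, vomiting, pleural effusions, aspiration pneumonia, bleeding), so the 28 entries are 28 − 7 = 21 differently worded events.

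**2. Does the exclusion reach grades 3 and 4?** Yes. Section 4.1.2 makes its exception within the sentence on grade 3 and higher events.

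**3. Does the investigator's override close the gap?** No. It is discretionary and sets no threshold. It joins nature, severity and frequency with 'and', so on a literal reading a severe event of expected nature and frequency stays out.

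**4. Cases side by side.** Each event is taken to be within 72 hours, at least possibly related, not serious and judged expected.

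| Event | Adverse event under the plan? | Collected under 4.1.2, 4.1.3, 4.3.1? | Owed to the 5.2.2 table? |
|---|---|---|---|
| Grade 3 bead allergy | Yes | Yes | Yes |
| Grade 3 right upper quadrant pain | Yes (5.1.1) | No | Yes |
| Grade 3–4 liver-test rise with symptoms, or treated, or considered clinically important | Yes (4.1) | No | Yes |
| Grade 3–4 liver-test rise with none of these features | 4.1: no; 5.1.1: arguably yes | No | Depends on which definition governs |

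Rows 2 and 3 are direct conflicts. Row 3 is the clearest for laboratory values, because the rule in section 4.1 makes the rise an adverse event and 4.1.3 then leaves it out. Row 4 is unsettled: section 4.1 lists the features that make an abnormal laboratory value an adverse event, while the general definition in 5.1.1 covers abnormal laboratory findings without those conditions.

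**5. Number of patients.** The plan gives no rate for any listed event, nor the share that would be related, judged expected and non-serious. No count of affected patients follows from the documents.

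**The case against.** The strongest defence is that the TAE and ablation lists describe effects of standard care, so those events are not related to the research and 5.2.2 does not ask for them. There is support for this. The stopping rule in 3.2.4 names TAE-related and research-related separately. Section 4.1.3 separates TAE events from bead events and sets grade 3 collection for the bead list. Section 9.5 says the device should add no risk beyond the clinically indicated procedure. But 4.3.1 describes the excluded events as coming from the research or the device and points to 4.1.3 for detail, and section 2.4 makes bead embolization the study arm. The defence may explain the intention; it does not reconcile the text.

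A second defence is that section 4.1 already covers laboratory values. It defines when such a value is an adverse event and how events are followed. It does not restore collection of what 4.1.3 excludes, so it sharpens row 3 of the comparison. It does weaken any claim resting on row 4: an asymptomatic, untreated rise that the investigator thinks unimportant may not be owed to the table at all.

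A third defence concerns importance, and it stands. The only objective is imaging, section 7.0 plans simple descriptive statistics, and no liver-safety rate is an endpoint. Section 5.2.2 keeps all serious events and all grade 5 events reportable whatever their cause. Hepatic panels are typically drawn daily in hospital (3.2.2), and changes in liver enzymes prompt further evaluation (9.5).

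**Conclusion.** The inconsistency is real and of low severity: a change to consider. By default 27 of 28 entries are kept out of the database at any grade, while 5.2.2 wants the related grade 3 and 4 events among them. The conclusion rests on reading 'related to the research' to include the study embolization, as 4.3.1 indicates.

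Three stronger readings are not supported.

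- A reader might infer that liver tests are a special case because the stopping rule counts only non-laboratory grade 4 toxicity. Other laboratory items in 4.1.3 (white cells, amylase and lipase, sodium, platelets and hemoglobin) are left out in the same way, and at grade 3 no listed item counts toward the three-patient limit.
- A reader might assume a rate of grade 3 or higher liver-test rises and present the chance of at least one as the chance of the conflict. That would be the chance of any such rise. The conflict also needs relatedness, a judgement that the rise is expected, and status as an adverse event, and the plan gives none of these rates. Confidence limits for zero events would likewise address a quantity the plan does not set out to estimate.
- A reader might infer a risk to patients or to enrollment decisions. The gap is in the dataset and the table; monitoring and the duty to report serious events remain.

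**What to change.** - **Section 4.1.3:** apply the grade 3 collection threshold already used for the bead list to the TAE and ablation lists, liver tests included. For liver tests, record the baseline grade as well, because section 2.1.1 admits ALT/AST up to 5 times the upper limit of normal, or 10 times with obstructive liver metastases. Changing only the two liver entries would leave the conflict in place for the other 25 of the 27.
- **Section 4.3.1:** amend the closing sentences of the toxicity definition so that only expected events below grade 3 are left uncollected.
- **Section 5.2.2:** state that grade 3 and 4 events collected under 4.1.3 feed the table, and say whether 4.1 or 5.1.1 decides when a laboratory rise counts as an adverse event.

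The cost is a few sentences and some record abstraction. No new tests or visits are needed, and the stopping rule need not change. The downside is that expected post-embolization events will appear in the adverse-event data; the baseline grade helps a reader to interpret the liver values.
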